## **2.8 Section 6.4 Run-in failure criteria**

*The Subject must be withdrawn from the trial during the run-in period if the following applies:*

1. *Included in the trial in violation of the inclusion and/or exclusion criteria.*
2. *Pregnancy*
3. *Intention of becoming pregnant*
4. *Participation in another clinical trial anytime during the run-in period*

*Subjects fulfilling any of the above criteria or withdrawing consent prior to randomisation are considered as run-in failures and should be completed as described in section 8.1.5.*

## **2.9 Section 6.6 Withdrawal criteria Criteria for premature discontinuation of trial product**

~~The subject may withdraw at will at any time.~~

The subject may be *discontinued from trial product withdrawn from the trial* at the discretion of the Investigator due to a safety concern.

The subject must be *discontinued from trial product withdrawn from the trial* if the following applies:

1. Included in the trial in violation of the inclusion and/or exclusion criteria and/or randomised in violation of the randomisation criterion
2. Pregnancy
3. Intention of becoming pregnant
4. Participation in another clinical trial ~~throughout~~ *anytime during* the trial

Subjects discontinued from trial product after randomisation will be followed as described in section 8.1.13.

## **2.10 Section 6.7 Withdrawal from Trial**

*The subject may withdraw consent at will at any time. The subject's request to withdraw from the trial must always be respected.*

*If the subject considers withdrawing consent the Investigator must underline to the subject the importance of continuing in the trial despite trial product discontinuation. If the subject agrees to discontinue trial product but to stay in the trial, procedures described in section 8.1.13 must be followed.*

*If a subject decides to withdraw informed consent the subject should be encouraged to undergo procedures as described in section 8.1.14.*

*A subject will be considered lost to follow-up if he/she repeatedly fails to attend the scheduled visits and the Investigator is unable to establish contact with the subject.*

*The following actions must be taken in relation to a subject who fails to attend the site for a required visit:*

- *The site must attempt to contact the subject and reschedule the missed visit as soon as possible*
- *The site must re-train the subject in the importance of maintaining the scheduled visits*

*In cases in which the subject is deemed lost to follow-up the investigator must make every effort to regain contact with the subject (e.g. telephone calls to friends or family members, e-mails or certified letter to the subject as applicable). These contact attempts must be documented in the subject's medical records. Should the subject continue to be unreachable, only then will he/she be considered to have withdrawn from the trial with the primary reason being "lost to follow-up"*

## **2.11 Section 6.6-6.8 Subject replacement**

Subjects who ~~are~~ withdraw~~n~~ or discontinue trial product will not be replaced.

## **2.12 Section 8.1.6 Randomisation**

Randomisation (Visit 10) must occur after 8 weeks ( $\pm 3$  days) of run-in. If the subject meets the randomisation criterion at Visit 10, then the subject will be randomised into one of the three treatment arms by using IV/WRS; please see details in section 10. Stop date of NovoRapid® and start date of the randomised trial product must be recorded *in the eCRF*.

## **2.13 Section 8.1.7 Site visits**

If a visit to the site is not performed as scheduled for any reason, then the Investigator should arrange for the visit to be performed as soon as possible and within the visit windows specified in section 2.

Scheduled dispensing should be performed at the visits indicated in the flowchart in section 2. A dispensing session must be performed in the IV/WRS when dispensing trial product. Drug accountability should be performed at each dispensing visit from Visit 10 until end of treatment(Visit 36).

## **2.14 Section 8.1.11 8.1.12 End of treatment**

At end of treatment (Visit 36) the randomised treatment with trial product must be discontinued and a completion IV/WRS session must be performed. ~~If the subject has completed treatment a completion session should be performed in IVRS.~~ The subject should be switched to a suitable marketed product at the discretion of the Investigator and this product must be recorded on the ~~Diabetes Treatment History~~ *concomitant diabetes medication* form in eCRF, as described in section 8.2.4. For procedures to be performed at end of treatment (Visit 36); please see flowchart in section 2. At end of treatment the *first treatment related* part of the end of treatment/trial form must be completed.

## **2.15 Section 8.1.12 8.1.13-Follow-up period**

The first follow-up visit (FU1) (Visit 37) is a site visit and must take place ~~no earlier than~~ 7-12 days after ~~the actual date of last day on trial product the end of treatment visit (Visit 36)~~. Follow-up Visit 2 (FU2) (Visit 38) is a phone contact and must take place ~~no earlier than~~ 30-35 days after the ~~last day on trial product end of treatment visit~~.

## **2.16 Section 8.1.13 Premature discontinuation of trial product**

*If a subject is prematurely discontinued from trial product after randomisation (Visit 10), the Investigator must ensure every possible effort is made to undertake procedures for Visit 36A, as soon as possible.*

*Treatment discontinuation must be performed in the eDiary web portal. This must be performed at least 4 days prior to Visit 36A to ensure scheduling of the 7-9-7-point profile on the three days prior to Visit 36A.*

*At visit 36A subjects must undergo the meal test before discontinuing trial product. The meal test should be performed with trial drug according to randomisation unless this is not feasible due to safety reasons including pregnancy as judged by the investigator. This must be documented in the eCRF.*

*A "treatment discontinuation" session must be made in the IV/WRS after the meal test has been completed and primary reason for discontinuation of trial product must be specified in the first part of the end-of-treatment/trial form in the eCRF.*

*Final drug accountability must be performed. The subject should be switched to a suitable marketed product at the discretion of the Investigator. The medication should be recorded on the concomitant diabetes medication form in the eCRF, as described in section 8.2.4 at each contact after trial drug discontinuation.*

*The subject should also complete the follow-up visits (visit 37 and phone contact 38). Visit 37 can be converted into a phone contact as collection of the eDiary is not applicable at this visit for the subjects that discontinue trial product prematurely.*

*In addition, subjects prematurely discontinued from trial product should continue with the per protocol planned visits at 4 (Visit 14), 8 (Visit 18), 12 (Visit 22), 16 (Visit 26), 20 (Visit 30), 24 (Visit 34) and 26 (Visit 36) weeks after randomisation depending on when the subject discontinues trial product. The meal test at V36 should be done with the subjects' currently prescribed insulin treatment with a bolus insulin dose of 0.1 U/kg. The eDiary must be returned to the site at the end of visit 36.*

*The following assessments are not applicable for subjects that prematurely discontinue trial product: 4 point profiles, daily doses of trial insulin, time of injection, duration of meal, titration method, dose recommendation, reason for deviation and collection of technical complaints.*

*In the following situations, only one visit should take place:*

- *If V36A is within 2 weeks of one of the per protocol planned visits, only V36A should be performed*
- *If any per protocol planned visit and the windows of a follow-up visit are overlapping according to visit schedule, only the per protocol planned visit should be performed*

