### General considerations

In general, for endpoints evaluated as a change from baseline and/or where a baseline adjustment is made, baseline is defined as information collected at the randomisation visit (Visit 10). In case a measurement is not available at the randomisation visit, the most recent measurement prior to the randomisation visit will be used as baseline.

*Two observation periods are defined, “in-trial” and “on-treatment”, and it will be specified which period each analysis will use.*

- *In-trial: the observation period from date of randomisation and until last trial-related subject-site contact. The in-trial observation period includes data collected after treatment discontinuation.*
- *On-treatment: the observation period from date of first dose of NovoRapid®/faster-acting insulin aspart and no later than 7 days after the day of last dose of NovoRapid®/faster-acting insulin aspart. The on-treatment observation period includes data collected up to and including 7 days after treatment discontinuation.*

*Analyses of efficacy endpoints will be based on the full analysis set (FAS). All efficacy endpoints will be summarised and analysed using the full analysis set (FAS), unless otherwise stated. Safety endpoints will be summarised using the safety analysis set (SAS) and analysed using the FAS.*

*Presentation of results from a statistical analysis will include the estimated mean treatment effects (LSMeans) for change from baseline, if applicable. Estimated mean treatment differences (or ratios) will be presented together with two-sided 95% confidence intervals for all endpoints analysed statistically.*

*For endpoints measured over time mean values will be plotted to explore the trajectory over time. For survival endpoints, e.g. drop-out pattern, Kaplan-Meier plots are presented for each treatment. Data collected before randomisation will only be summarised descriptively.*

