### **Primary Estimand (de facto)**

*The primary estimand is defined as the treatment difference between subjects randomised to faster-acting insulin aspart and NovoRapid® both in combination with insulin degludec, in adults with type 1 diabetes assessed by change from baseline in HbA1c 26 weeks after randomisation for all randomised subjects regardless of treatment discontinuation or use of ancillary therapies. This estimand is a de facto estimand addressing effectiveness.*

*The primary estimand assesses the expected glycaemic benefit a future population with type 1 diabetes can achieve if prescribed to faster-acting insulin aspart as compared to NovoRapid®. By not putting any restrictions on the treatment adherence, this estimand aims at a difference as close as possible to the one that can be expected in real-world clinical practice, provided that the*

*treatment adherence and use of ancillary therapies reflect clinical practice. Thereby the primary estimand provides a treatment difference for clinicians concerning the glycaemic effect of faster-acting insulin aspart compared to NovoRapid® in the day to day life in individual subjects with type 1 diabetes in an adult population.*

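### Does the one-visit rule in Section 8.1.13 wrongly cost the trial its week-26 value in subjects who stop trial product late?

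*Protocol*

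**What the plan says.** Amendment 2 separates stopping trial product from leaving the trial. Under Section 8.1.13, a subject who stops after randomisation has a V36A visit and then keeps to the planned visits, the last of them at weeks "24 (Visit 34) and 26 (Visit 36) weeks after randomisation depending on when the subject discontinues trial product". Two exceptions follow, under the lead-in "In the following situations, only one visit should take place". The first bullet sets V36A against a planned visit: "If V36A is within 2 weeks of one of the per protocol planned visits, only V36A should be performed". The second sets a planned visit against a follow-up visit: where a planned visit and the "windows of a follow-up visit are overlapping according to visit schedule, only the per protocol planned visit should be performed".

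The two visits use different insulin for the meal test. At the discontinuation visit, "At visit 36A subjects must undergo the meal test before discontinuing trial product", normally with the randomised product. At Visit 36 a subject who has already stopped takes the test on the "currently prescribed insulin treatment with a bolus insulin dose of 0.1 U/kg".

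In Section 17, the primary estimand is the HbA1c change "26 weeks after randomisation for all randomised subjects regardless of treatment discontinuation or use of ancillary therapies", and both estimands are repeated for the 1-hour meal-test increment and 1,5-anhydroglucitol. For the secondary estimand, "The on-treatment observation period includes data collected up to and including 7 days after treatment discontinuation".

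**The concern.** Three things make the rule look wrong.

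- **The estimand.** Amendment 2 exists largely to obtain week-26 values from subjects who have stopped treatment. The first bullet, read literally, tells sites not to collect that value from a consenting subject who stops in the last two weeks. Section 17.3 foresees missing data from withdrawn consent or loss to follow-up, not from a visit the protocol itself removes. It also says that imputing from subjects who stop treatment but stay in the trial will not be feasible.
- **The spacing.** Two weeks is half the gap between planned visits up to week 24, but the whole gap between Visit 34 and Visit 36. One late V36A can stand in for both.
- **The second bullet.** It can retain a planned visit on some of the same days, and no order of application is given, so two sites might act differently.

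At stake would be off-treatment week-26 data for steps 1, 2 and 4 (HbA1c), step 3 (meal test) and step 5 (1,5-anhydroglucitol). A sample never taken cannot be recovered at the analysis stage.

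**Working it through.** **Inputs.** Randomisation is day 0. From the amended flow chart, Visit 34 is day 168 (window 165 to 171) and Visit 36 is day 182 (window 179 to 185). Follow-up visit 1 is 7 to 12 days, and follow-up visit 2 is 30 to 35 days, after the last day on trial product; I take that day to be the V36A day, t. Section 17.1 gives 999 subjects, 333 per arm, treatment discontinuation that might be as low as 8%, with half of those also leaving the trial, and a margin of 0.4.

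**Days on which Visit 36 is displaced.** |182 − t| ≤ 14 with t before the Visit 36 window gives t = 168 to 178, which is 11 days. V36A then precedes nominal week 26 by 182 − 178 = 4 to 182 − 168 = 14 days. On t = 168 to 171 (4 days) V36A also lies in the Visit 34 window.

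**Do the bullets conflict?**
- Follow-up visit 1 (t+7 to t+12) meets the Visit 36 window for t = 167 to 178, and meets nominal day 182 for t = 170 to 175. The second bullet can therefore be invoked on all 11 days, or on 6.
- That bullet decides only whether a planned visit or a follow-up visit is held. It does not restore a planned visit that V36A has already replaced, and V36A comes first in time.
- It has work of its own elsewhere. Follow-up visit 2 meets the Visit 36 window for t = 144 to 155, where the first bullet does not reach Visit 36.
- Between weeks 4 and 24 planned visits are 28 days apart, so some planned visit is always within 28/2 = 14 days of V36A. That fits a general rule that V36A stands in for a neighbouring visit.

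**Subjects affected**, assuming stopping times uniform over 182 days (the protocol gives no distribution):
- Stopped but retained: 0.04 × 999 × 11/182 = 2.4.
- If all who stop were retained: 0.08 × 999 × 11/182 = 4.8.
- If 3% to 12% of stops fell in these days: 0.04 × 999 × 0.03 = 1.2 to 0.04 × 999 × 0.12 = 4.8.
- If both discontinuation rates doubled: 0.08 × 999 × 11/182 = 4.8 retained.

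**How many would give a clearly off-treatment value at Visit 36?** The on-treatment period runs 7 days past the last dose. Even the earliest Visit 36 (day 179) is outside it only if 179 − t > 7, so t ≤ 171. That leaves days 168 to 171: 0.04 × 999 × 4/182 = 0.9 subjects, at most 1.8. On days 172 to 177 it depends on where in the window Visit 36 falls. On day 178 Visit 36 is always inside the period.

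**Effect if the value is lost.** The plan's step 1 and step 2 powers come first. The tracked-change digits run together; I read SD 1.2, 99.0% and 89.6%. For a two-group t-test, one-sided 2.5%, noncentrality = (0.4 − difference)/(1.2 × √(2/n)):
- n = 333: 0.4/0.0930 = 4.30 gives 99.02%, and 0.3/0.0930 = 3.23 gives 89.64%. Both stated figures are reproduced.
- n = 331: 98.99% and 89.46%.

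Losing 2 per arm is 6 subjects in all, more than the 4.8 above.

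**Effect if the V36A HbA1c is used instead.** There are 2.4/3 = 0.8 affected subjects per arm (1.6 at most). Assume HbA1c would have moved by up to 0.5 points between the visits. The arm mean shifts by 0.8 × 0.5/333 = 0.0012, at most 1.6 × 0.5/333 = 0.0024.

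**Meal test.** The same subjects carry 0.8/333 = 0.24% of an arm, at most 1.6/333 = 0.48%. For each 1 mmol/L by which the two tests differ in an affected subject (an assumed difference), the arm mean moves 0.002 to 0.005 mmol/L.

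**The case for a change.** The best argument for changing the text is that this is an instruction to sites, so an analysis plan cannot repair it, and that other parts of Amendment 2 assume Visit 36 happens. The eDiary is to be handed back at the end of Visit 36. Section 8.1.14 asks even a discontinued subject who later withdraws consent to undergo the Visit 36 procedures. It seems odd to ask less of a subject who stays.

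Part of this stands. The first bullet does not say whether it is meant to reach Visit 36, and where it does, no visit is named for returning the eDiary. The meal tests are also not equivalent, since one uses randomised product and the other current insulin.

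The rest is weaker. The Section 8.1.14 provision concerns subjects who have already completed follow-up visit 2, at least 30 days after the last dose. For a V36A on day 168 that is day 198 or later, after the Visit 36 window has closed, so it says nothing about late stoppers. Nor is it true that nothing is collected: V36A is a full assessment with a meal test and a 7-9-7-point profile. Its HbA1c cell cannot be read reliably in the extracted flow chart, so HbA1c at V36A is assumed. Holding both visits would mean two fasting 4-hour meal tests 4 to 14 days apart. Sparing subjects that is a reasonable trade-off, and whether the second test is worth the burden is for the sponsor to judge.

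**Conclusion.** No change is needed. It is true that Visit 36 is not exempt and that a V36A on days 168 to 178 replaces it. The alleged conflict between the bullets does not hold, because they rank different pairs of visits. For HbA1c, the only firm gain from an exemption would be a second sample 4 to 14 days after the first, in about 2 of 999 subjects, of whom about 1 would be certain to be off treatment by the plan's 7-day definition. Section 3.6 of the protocol itself describes HbA1c as a measure of long-term control, so little movement over that interval is to be expected. Deciding which scheduled week the V36A value represents is a mapping question that an analysis plan ordinarily settles.

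The conclusion rests on four assumptions: stopping times roughly uniform, 4% of subjects stopping treatment but staying in the trial, HbA1c measured at V36A, and no more than 0.5 points of change between the visits. It is not sensitive to the first two, since a stop share of 12% in these days, or a doubling of the discontinuation rates, still gives about 5 subjects. If V36A supplied no HbA1c, the loss-of-subjects calculation applies and costs less than 0.2 percentage points of step 2 power. No conclusion in steps 1 to 5 is shown to be at risk. At most, a future edit could say in a few words whether the rule is meant to cover Visit 36.

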***eDiary records after premature discontinuation of trial product:***

*Date, actual clock time and value of the SMPG measurements performed as part of the 7-9-7-point profiles on the three consecutive days prior Visit 36A, Visit 22 and Visit 36*

*For hypoglycaemic episodes only the following information should be recorded from visit 36A and onwards:*

- *Start date and time of hypoglycaemic episode*
- *Value of plasma glucose level before treating the episode (if available) and any follow up measurements.*
- *Whether the episode was symptomatic (Yes/No)*
- *Whether the subject was able to treat him/herself*

**2.17 Section 8.1.14-8.1.11 Withdrawals Withdrawal from trial**

If a subject is ~~withdrawn~~ withdraws informed consent from the trial, the Investigator must aim to undertake procedures similar to those for Visit 36 including the meal test, as soon as possible and the follow up visits (Visit 37 and 38). *The Investigator must encourage the subjects to undergo the meal test at Visit 36. The meal test must be performed with trial drug according to randomisation unless this is not feasible due to safety reasons including pregnancy as judged by the investigator.*

The end of treatment/trial form must be completed *in the eCRF* and final drug accountability must be performed even if the subject is not able to come to the trial site. A ~~withdrawal session~~ “treatment discontinuation” session must be made in the IV/WRS. ~~and the case book must be signed.~~

Although a subject is not obliged to give his/her reason(s) for withdrawing from a trial, the Investigator must make a reasonable effort to ascertain the reason(s), while fully respecting the subject's rights. Where the reasons are obtained, the primary reason for *discontinuing trial product and not completing the trial* must be specified on the end of treatment/trial form in the eCRF *and the case book must be signed.*

*In case a premature discontinuation subject chooses to withdraw consent from trial after completing Visit 36A, FU1 and FU2, the Investigator must encourage the subjects to undergo procedures of Visit 36 whereas FU1 and FU2 visit are not to be completed again.*

**2.18 Section 8.2.1 Demography**

The following demographic data will be obtained by the Investigator and recorded:

- Date of birth (if not permitted according to local laws the year of birth will be collected)
- Ethnicity (if permitted according to local laws)

- Race (if permitted according to local laws)
- Sex

~~The Investigator must document whether females are of non-childbearing potential in the subject's medical record and in the eCRF.~~

*It must be recorded in the CRF whether female subjects are of childbearing potential.*

*Female of non-childbearing potential is defined as:*

- *Female who has undergone a hysterectomy, bilateral oophorectomy or bilateral tubal ligation*
- *Postmenopausal defined as no menses for 12 months without an alternative medical cause*
- *Other medical reasons preventing childbearing potential*

*Pregnancy testing must be performed as described in Section 8.5.2.4.*

*The subjects must be instructed to use contraceptive methods throughout the trial and until 1 week after end of treatment.*

## **2.19 Section 8.3.1 Meal test**

Time point 0 is defined as the time when the subject starts the consumption of the liquid meal. The subject will have a carbohydrate-rich standardised liquid meal served. The standardised liquid meal must be consumed as quickly as possible and within 12 minutes. The Investigator should confirm that the subject consumed the required volume of the standardised meal in the eCRF and actual clock time of injection and *actual clock time of the start of the meal consumption* should be noted.

The standardised meal will be provided by Novo Nordisk. The volume of the standardised meal to be consumed should be measured out by the Investigator to be the equivalent to 80 78 gram of carbohydrate. The amount of mL of the standardised meal may differ from country to country.

